## **C. Day 1 of Each Cycle**

- Physical exam, including weight
- CBC with differential and platelets
- Serum chemistries, including albumin, creatinine, total bilirubin, AST, ALT, LDH

## **D. All Cycles Days 1-10**

Decitabine administration, 20 mg/m^2/day will be given as a 1-hour continuous intravenous infusion. Decitabine dose will be calculated on baseline weight (obtained within a week of the start of Cycle 1). Decitabine dose only should be recalculated for weight changes at the beginning of each cycle that are above or below 10% from baseline weight.

Decitabine may be reduced to Days 1-5 after Cycle 2 or Days 1-3 after Cycle 4. See Section 6 for details.

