### **5.0 INVESTIGATION PLAN**

#### **5.1 Summary**

See Section 10 for synoptic table.

Patients will receive decitabine 20 mg/m^2/day as a 1-hour infusion on consecutive days 1-10 of each 28-day cycle. Decitabine dose will be calculated on baseline weight (obtained within a week of the start of cycle 1). Decitabine dose should be recalculated for weight changes above or below 10% from baseline weight

Patients with clinical evidence of progressive disease or relapse (see Section 12 for definitions) should undergo a bone marrow biopsy to evaluate for progression.

After 2 cycles, patients with progressive disease or relapse (a clear progression with at least >20% bone marrow blasts and an increase of at least 50% from prior biopsy) should be removed from protocol and proceed to salvage treatment according to center preference.

Transplant eligible patients with PR after 3 cycles, may be removed from protocol and proceed to salvage treatment or transplant according to center preference.

Transplant eligible patients with a suitable donor who achieve mLFS, CR, CRc, or CRi, may proceed to transplant after at 3 cycles (Section 5.5).

Transplant ineligible patients with CR, CRc or CRi, PR will continue on maintenance doses (see below and Section 6.3) until progression or death, whichever occur first.

Transplant ineligible patient with SD after cycle 4 may be removed from protocol and proceed to alternative treatment or continue on protocol according to treating physician's preference.

After Cycle 1, patients with blast counts < 5% may reduce decitabine dose from 20 mg/m^2/day x 10 days to 20 mg/m^2/day x 5 days.

For all other patients, after Cycle 2, decitabine administration dose will be decreased to 20 mg/m^2/day for 5 consecutive days (Days 1-5) every 28 days (unless otherwise specified) to limit myelosuppressive toxicity.

Peripheral blood sampling and bone marrow biopsies with aspirate will be performed pre-study, on Cycle 1 Day 10 ± 2, Cycle 1 Day 28 ± 4, on Cycle 2 Day 28 ± 4, on Cycle 3 Day 28 ± 4, and at progression or relapse. Patients will provide a skin biopsy sample pre-study; a buccal swab can be performed for patients who decline skin biopsy. A buccal swab will be collected on Cycle 2 Day 28 ± 4.

Following Cycle 3, bone marrow biopsies should be performed at the discretion of the treating physician to assess for response and for relapse or progression.

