### **5.3 Agent Administration**

Cycle 1: All patients will receive decitabine 20 mg/m^2 IV infusion per day over one hour on Days 1-10 of a 28-day cycle.

Cycle 2: Patients with bone marrow blast counts < 5% may receive decitabine 20 mg/m^2 IV infusion per day over one hour on Days 1-5 of a 28-day cycle. All other patients will receive decitabine 20 mg/m^2 IV infusion per day over one hour on Days 1-10 of a 28-day cycle.

Cycle 3 and subsequent cycles: All patients will receive 20 mg/m^2 IV infusion per day over one hour on Days 1-5 of the 28-day cycle

Patients will continue on therapy until time of transplantation or progression as detailed in Sections 5.1 and 6.3. Delays in therapy are permitted due to infection and other complications.

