### **6.3 Modification in Dose or Schedule**

To limit myelosuppressive toxicity, Cycles 3 and beyond will consist of 20 mg/m^2/day for 5 consecutive days (Days 1-5).

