## 10.0 STUDY CALENDAR

	Screening	B/I	C1D1	C1D0	C1D28	C2D1	C2D28	C3D1	C3D28	All cycles thereafter		Time of progression	F/U
										D1	D28		
Informed consent	X												
Medical history	X		X			X		X		X			
Physical exam, ht, wt	X	X 	X			X		X		X		X	
CBC + diff	X	X 	X	-----	X 	X 	X	X 	X	X 		X	
Serum chemistry 	X	X 	X			X		X		X		X	
Pregnancy test 	X	X 											
HIV, hepatitis tests	X 												
BM bx + aspirate 				X 	X 		X 		X 		X 	X	
Flow cytometry 													
PB for research				X 	X 		X 		X 			X	
Skin biopsy													
Buccal swab							X						
Decitabine			X	----	X 		X 		X 		X 		
AE assessment													
Progression/survival													X 

1. Women of childbearing potential only
2. On bone marrow or peripheral blood
3. For BMBX, no more than 28 days prior to the 1st dose of decitabine. For the skin biopsy, if WBC at enrollment is > 30,000/ $\mu$ l, the skin biopsy should be collected during C1D28, or thereafter.
4. No more than 7 days prior to the 1st dose of decitabine
5. Including albumin, creatinine, total bilirubin, AST, ALT, LDH
6. Days 1-10
7. May be reduced to Days 1-5 for Cycles 3 and 4
8. Buccal swab may be performed at baseline in patients who decline skin biopsy
9. Drawn weekly during Cycle 1; may be reduced to Days 1 and 15 of each cycle after Cycle 1
10. Patients who relapse or who have progressive disease (PD) after 2 cycles of decitabine may proceed to alternative salvage regimen or to stem cell transplant per treating physician and center preference.
11. Transplant eligible patients who achieve CR, CRc, CRi, or mLFS after 3 cycles with a suitable donor will proceed to conditioning regimen and transplant; transplant eligible patients who are in PR after 3 cycles will be removed from protocol and proceed to salvage treatment according to center preference; transplant ineligible patients with all responses (CR, CRc or CRi, PR, SD) will continue on maintenance doses until progression or death
12. At the discretion of the treating physician
13. +/- 2 days, only patients enrolled at Washington University

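### Section 5.1.D and the calendar notes conflict with the schema, 5.1, 5.3 and 6.3 on decitabine days after Cycle 1, and the Days 1-3 option refers to a rule that Section 6 does not contain

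*Combined protocol and SAP*

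**What the plan says.** Six places in the protocol set decitabine days per cycle after Cycle 1, and they fall into two groups.

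**Reduction stated as the rule.** The schema applies the five-day schedule to every patient after Cycle 2. The later text of 5.1 first gives an option after Cycle 1, "After Cycle 1, patients with blast counts < 5% may reduce decitabine dose from" ten days to five, and then continues "For all other patients, after Cycle 2, decitabine administration dose will be decreased to" the five-day schedule. Section 5.3 assigns all patients, from Cycle 3 onward, an "IV infusion per day over one hour on Days 1-5 of the 28-day cycle". Section 6.3 says "To limit myelosuppressive toxicity, Cycles 3 and beyond will consist of" five consecutive days.

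**Reduction stated as an option.** Section 5.1.D, whose heading refers to Days 1-10 in all cycles, says "Decitabine may be reduced to Days 1-5 after Cycle 2 or Days 1-3 after Cycle 4" and points to Section 6 for details. Calendar note 7 (Section 10) says "May be reduced to Days 1-5 for Cycles 3 and 4". Calendar note 6 gives Days 1-10 with no exception for blast count.

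**The concern.** A site working from the procedure list in 5.1.D or from the calendar could give a ten-day course in Cycle 3, or a three-day course in Cycle 5. Sections 5.3 and 6.3 allow neither. No passage says which text takes precedence.

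Three things are at stake.

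- **Safety.** Sections 5.1 and 6.3 give limiting myelosuppression as the reason for shortening the course. Two passages make that protection discretionary. Later cycles matter because Section 5.8 lets transplant-ineligible patients continue without a fixed limit.
- **Compliance.** Section 14 audits protocol adherence, Appendix C makes major deviations reportable, and Section 7.5.F lists overdose and medication error as special situations. Sites cannot classify the same course consistently while the passages disagree.
- **Interpretation.** This is a single-arm multicenter trial, and Section 15.3 plans no analysis by center. The disposition summary in 15.4.A counts cycles, not dosing days. Differences arising from different readings would not show in those summaries.

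**Working it through.** The plan states no figure to reproduce. The check sets the passages side by side and then converts days to dose. Entries are dosing days per cycle.

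| Source | Cycle 2 | Cycles 3-4 | Cycle 5 onward |
|---|---|---|---|
| Schema | 10; 5 optional if blasts < 5% | 5, all patients | 5, all patients |
| 5.1, later paragraphs | 10; 5 optional if blasts < 5% | 5 | 5 |
| 5.3 | 10; 5 optional if marrow blasts < 5% | 5, all patients | 5, all patients |
| 6.3 | not addressed | 5 | 5 |
| 5.1.D | 10; no option stated | 10, or 5 by option | 10, or 5 or 3 by option |
| Calendar notes 6-7 | 10; no option stated | 10, or 5 by option | no reduction named |

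Cycle 1 is ten days throughout.

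**The cross-reference.** Section 6.0 covers a delay of more than 12 weeks between cycles. Section 6.1 covers cytopenia and infection; its only dose change is a halved daily dose in Cycle 2, still over ten days. Section 6.2 covers organ dysfunction and non-hematologic toxicity, again by delay or a halved daily dose. Section 6.3 gives five days from Cycle 3. None contains a three-day schedule, a change after Cycle 4, or criteria for who would receive one.

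**Dose per cycle.** Dose = 20 mg/m2/day x days:

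- 10 days: 20 x 10 = 200 mg/m2
- 5 days: 20 x 5 = 100 mg/m2
- 3 days: 20 x 3 = 60 mg/m2

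**Size of the conflict.**

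- Cycles 3-4: 200 / 100 = 2-fold.
- Cycle 5 onward, the conflict specific to the three-day sentence: 100 / 60 = 1.7-fold.
- Cycle 5 onward, widest literal range: 200 / 60 = 3.3-fold.

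**Cumulative illustration.** The protocol fixes no number of cycles, so six is an assumption. Total dosing days are:

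- Schema, 5.3 and 6.3, no early reduction: 10 + 10 + 5 + 5 + 5 + 5 = 40
- Schema and 5.3, reduced from Cycle 2: 10 + 5 + 5 + 5 + 5 + 5 = 35
- 5.1.D with both options used: 10 + 10 + 5 + 5 + 3 + 3 = 36
- 5.1.D with no option used: 10 x 6 = 60

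The literal readings therefore run from 35 to 60 dosing days over six cycles.

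**The case against.** The strongest reply is that most of the protocol is clear. The schema, later 5.1, 5.3 and 6.3 agree with each other from Cycle 3, and a careful site would follow them. A reader might infer that all the dosing sections contradict one another; they do not. The outliers are 5.1.D and the calendar notes. This part of the reply stands.

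A reader might also treat the opening of 5.1, "infusion on consecutive days 1-10 of each 28-day cycle", as a further competing schedule. It is better read as a general statement that the same section goes on to qualify. The heading of 5.1.D is likewise qualified by the text under it. Neither is relied on here as a separate contradiction.

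It is tempting to say that the calendar restricts the reduction to two cycles. Note 7 names Cycles 3 and 4, but it does not exclude later ones. Marker 7 appears twice in the decitabine row, and the table layout is too damaged in the available text to place it. What can be said is that note 7 mentions no later cycle.

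Finally, 5.1 allows for exceptions specified elsewhere, which might be thought to cover the three-day course. Sections 5.3 and 6.3 contain no such allowance, and the section cited for details has none to give. The agreement of four passages does not settle the matter: the procedure list and the calendar are operational texts that sites would reasonably use.

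**Conclusion.** The inconsistency is real, and it is limited to cycles after the first. It has three parts: five days from Cycle 3 is the rule in four places and an option in two; the three-day schedule appears only in 5.1.D with an empty reference to Section 6; and the Cycle 2 option for low blast counts is missing from 5.1.D and calendar note 6.

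The size is 2-fold per cycle in Cycles 3-4. From Cycle 5 it is 1.7-fold, or 3.3-fold at the extreme. The 3.3-fold figure cannot arise earlier, because no passage allows three days before Cycle 5. It also requires one site to leave every option in 5.1.D unused while another uses the three-day option. These figures assume the full daily dose and literal reading of each passage.

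A reader might infer that the regimen behind the 1-year OS result is undefined. The documents do not support that. Cycle 1 is consistent, the primary objective covers patients given at least one dose, and individual exposure already varies by plan through the discretionary reductions in 6.1 and 6.2 and the Cycle 2 option. Transplant-eligible responders may leave for transplant after three cycles, so the three-day issue reaches only those still dosed after Cycle 4. The documents give no number for that group, so any effect on 1-year OS cannot be quantified. No sample-size, power or analysis figure changes. The contradiction should still be corrected, because it bears on patient exposure and deviation reporting.

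**What to change.** The sponsor should reconcile 5.1.D and calendar notes 6 and 7 with the schema, 5.1, 5.3 and 6.3, so that each cycle has one stated schedule. For each reduction, the text should say whether it is optional or mandatory, which cycles it covers and which patients it applies to. The reference from 5.1.D to Section 6 should be resolved, so that the two sections say the same about a Days 1-3 schedule. Which schedule is right is for the sponsor to decide.

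The cost is one clarifying protocol amendment, with the usual IRB submission and distribution to secondary sites under Section 16. It needs no change to the sample size, the analysis or data collection.

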## **E. Cycle 1 Day 10 $\pm$ 2**

Bone marrow aspirate and biopsy. Standard bone marrow procurement procedures will be followed for collection of the tissue. Assessments performed on bone marrow will include correlative studies and morphologic assessment. Bone marrow aspirate and biopsies at this time point will only be performed in patients enrolled at Washington University.

## **F. Weekly**

CBC with differential and platelets. After the first cycle, this may be changed to every other week at the discretion of the treating physician.

### **G. At the Discretion of the Treating Physician**

Serum chemistries, such as bicarbonate, calcium, glucose, total protein, albumin, BUN, potassium, chloride, sodium, creatinine, total bilirubin, AST, ALT, alkaline phosphatase, LDH.

Transfusions should be performed at the discretion of the treating physician and are permitted at any time during the protocol.

### **H. Cycles 1, 2, and 3 Day 28 ± 4**

- Bone marrow aspirate and biopsy. Standard bone marrow procurement procedures will be followed for collection of the tissue. Assessments performed on bone marrow will include: correlative studies, morphologic assessment, cytogenetics, and FISH.
- CBC with differential and platelets

### **I. End-of-Study Procedures**

- Physical exam.
- CBC with differential and platelets.
- Serum chemistries albumin, creatinine, total bilirubin, AST, ALT, and LDH.
- Bone marrow aspirate and biopsy. Standard bone marrow procurement procedures will be followed for collection of the tissue. Assessments performed on bone marrow will include morphologic assessment, cytogenetics, and FISH.

### **J. Post-study Follow-up**

Patients are to be followed according to standard patient care procedures for 30 days following the date of the last decitabine dose to monitor for toxicity, survival, and response. Thereafter, the investigator or designee will record information on subsequent therapy, disease progression, and/or death every 6 months for 2 years after last dose of study drug or until the patient is lost to follow-up or dies.

## **5.2 Premedication Administration**

Patients may be premedicated with lorazepam, prochlorperazine, palonosetron, granisetron, or ondansetron at the treating physician's discretion before decitabine infusion.

### **5.3 Agent Administration**

Cycle 1: All patients will receive decitabine 20 mg/m^2 IV infusion per day over one hour on Days 1-10 of a 28-day cycle.

Cycle 2: Patients with bone marrow blast counts < 5% may receive decitabine 20 mg/m^2 IV infusion per day over one hour on Days 1-5 of a 28-day cycle. All other patients will receive decitabine 20 mg/m^2 IV infusion per day over one hour on Days 1-10 of a 28-day cycle.

Cycle 3 and subsequent cycles: All patients will receive 20 mg/m^2 IV infusion per day over one hour on Days 1-5 of the 28-day cycle

Patients will continue on therapy until time of transplantation or progression as detailed in Sections 5.1 and 6.3. Delays in therapy are permitted due to infection and other complications.

### **5.4 Relapsed or Progressive Disease**

Patients who relapse or who have progressive disease (PD) after 2 cycles of decitabine, may proceed to alternative salvage regimen or to stem cell transplant according to treating physician and to center preference. (Please refer to Section 12 for the definition of PD.)

### **5.5 Transplantation**

Patients in mLFS, CR, CRc, or CRi who are considered fit for stem cell transplantation and who have an appropriate donor will undergo stem cell transplantation per treating physician recommendations. Haploidentical and allogenic transplantation may be utilized. Myeloablative and non-myeloablative protocols may be utilized per institutional protocols. Patients will be considered on study through day of transplant and will be followed for overall survival.

### **5.6 Women of Childbearing Potential**

Women of childbearing potential (defined as women with regular menses, women with amenorrhea, women with irregular cycles, women using a contraceptive method that precludes withdrawal bleeding, and women who have had a tubal ligation) are required to have a negative serum/urine pregnancy test within 7 days prior to the first dose of the study agent.

Female and male patients (along with their female partners) are required to use two forms of acceptable contraception, including one barrier method, during participation in the study and for 6 months following the last dose of the study agent.

If a patient is suspected to be pregnant, the study agent should be immediately discontinued. In addition, a positive urine test must be confirmed by a serum pregnancy test. If it is confirmed that the patient is not pregnant, the patient may resume dosing.

If a female patient or female partner of a male patient becomes pregnant during therapy or within 6 months after the last dose of the study agent, the investigator must be notified in order to facilitate outcome follow-up.

## **5.7 Concomitant Therapy and Supportive Care Guidelines**

### **A. Chemotherapy**

Patients may be receiving hydroxyurea at enrollment and may continue on hydroxyurea through Cycle 2 of decitabine. An indication for hydroxyurea following 2 cycles of decitabine is evidence that the patient is not responding and decitabine should be discontinued. Other than decitabine, patients cannot receive chemotherapy during this trial.

### **B. Growth Factors**

Erythroid growth factors should not be routinely administered to patients during the study.

Thrombopoietin receptor agonists should not be routinely administered to patients during the study.

Filgrastim (G-CSF) or sargramostim (GM-CSF) may be administered to patients with septic shock or febrile neutropenia at the discretion of the treating physician.

### **C. Transfusions**

RBC transfusions and platelet transfusions will be administered at the discretion of the treating physician.

### **D. Prophylactic Antimicrobial Agents**

Antimicrobial agents will be administered at the discretion of the treating physician. Common antimicrobial prophylaxis includes acyclovir, ciprofloxacin, and fluconazole. Alternative antibacterial and antifungal agents (e.g. voriconazole or posaconazole) may be used at the discretion of the treating physician.

Administration of live or attenuated vaccination is not permitted.

### **E. Radiotherapy**

Patients cannot receive radiotherapy within 14 days prior to study enrollment or while on study.

### **F. Plasmapheresis or other anti-cancer therapy**

The use of plasmapheresis, other anti-cancer therapies, or other investigational agents is not permitted.

## **5.8 Duration of Therapy**

If at any time the constraints of this protocol are considered to be detrimental to the patient's health and/or the patient no longer wishes to continue protocol therapy, the protocol therapy should be discontinued and the reason(s) for discontinuation documented in the case report forms.

In the absence of treatment delays due to adverse events, treatment may continue until the start of conditioning therapy for transplant or, in transplant ineligible patients, treatment may continue indefinitely or until one of the following criteria applies:

- Documented and confirmed disease progression
- Death
- Adverse event(s) that, in the judgment of the investigator, may cause severe or permanent harm or which rule out continuation of study drug
- General or specific changes in the patient's condition render the patient unable to receive further treatment in the judgment of the investigator
- Suspected pregnancy
- Serious non-compliance with the study protocol
- Lost to follow-up
- Patient withdraws consent
- Investigator removes the patient from study
- The Siteman Cancer Center decides to close the study

Patients who prematurely discontinue treatment for any reason will be followed as indicated in the study calendar.

## **5.9 Duration of Follow-up**

Patients will be followed with regular office visits for at least 2 years since enrollment or until death, whichever occurs first.

## **6.0 DOSE DELAYS/DOSE MODIFICATIONS**

A criterion for discontinuation of the study is a delay of > 12 weeks between any two cycles. Dose delays and modifications are allowed as specified below.

### **6.1 Delay for Cytopenia or Infection**

As cytopenias are a defining feature of AML, their presence alone does not warrant dose modifications or delays. Patients will receive two cycles of therapy without adjustment for any cytopenia. Following Cycle 2, dose delays for cytopenias will be made at the discretion of the investigator in patients who have had significant infection complications.

In patients with febrile neutropenia (temperature  $\geq 38.5^\circ$  with ANC  $< 1,000/\mu\text{l}$ ) or systemic infections, treatment will be held at discretion of treating physician.

In patients who experience significant infection complications during Cycle 1, Cycle 2 may be reintroduced with a 50% dose reduction (10 mg/m^2/day for 10 consecutive days), or at full dose at the discretion of the investigator.

### **6.2 Delay for Organ Dysfunction**

If renal dysfunction (creatinine  $\geq 3 \times$  IULN) or hepatic dysfunction (bilirubin  $\geq 2.5$  mg/dl or ALT/AST  $\geq 3 \times$  IULN) occurs, therapy may not resume until the abnormalities have resolved to below the limits stated above. If renal or hepatic dysfunction occurs during a treatment course, the next dose of decitabine should be held, and serum chemistries should be checked twice per week. Decitabine can be resumed at full dose when creatinine, bilirubin, ALT and AST are below the limits listed above.

For grade 3-4 non-hematologic toxicities related to decitabine, decitabine treatment should be delayed until recovery to baseline or to grade  $\leq 1$ . Decitabine may be reintroduced with a 50% dose reduction (10 mg/m^2/day), or at full dose at the discretion of the investigator.

